Illness perception	Brief Illness Perception Questionnaire	8 items; 10 point Likert scale, scoring 1 – 10.	Broadbent E, et al. J Psychosom Res 2006;60:631-7	20
Quality of life	Pediatric Quality of Life (PedsQL)	23 items; 5 point Likert scale scored 0 – 4, and then multiplied with 25 to get a 100 point scale; average score reported. Four subdomains: health related, emotional, social, school.	Varni JW, et al. Health and quality of life outcomes 2007;5:9.	19
Interoception	Body Vigilance Scale (BVS)	4 items; 11 point Likert scales 0 – 10. Score on item 3 should be divided by 10. Scores on item 4: average among 15 sensations. Total sum score range 0 to 40.	Schmidt NB, et al. J Consult Clin Psychol 1997; 65: 214-20.	21
Miscellaneous/hypotheses generating	Self-invented	a) 1 item addressing avoidance behavior: “To what degree do you avoid everything that may worsen your symptoms”? b) 1 item addressing school absenteeism.		20/22
CONSTITUTIONAL				
Neuroticism	NEO-FFI-30	6 items making up the neuroticism axis; 5-point Likert scale scored 0 – 4. Total sum score range 0 – 24.	Körner A, et al. Psychother Psychosom Med Psych. 2008; 58: 238-245	24

Worrying tendencies	Penn State Worry Questionnaire (PSWQ)	16 items; 5-point Likert scale scored 1 – 5 (reversed scoring of item 1,3,8,10,11). Total sum score range 16 to 80	Pallesen, S, et al. Scandinavian Journal of Psychology 2006, 47, 281–291	25
Emotional awareness	Toronto Alexithymia Scale (TAS-20)	7 items making up the index of Difficult identifying feelings. 5-point Likert scale scored 1-5, total sum score range 7 to 49.	Bagby RM, et al.. J Psychosom Res 1994;38:33-40.	23
Loneliness	UCLA loneliness scale	20 items; 4-point Likert scale scored 1 – 4 (reverse scoring of item 1,5,6,9,10,15,16,19,20). Total sum score from 20 to 80.	Russell, D., et al. Journal of Personality and Social Psychology 1980, 39(3), 472–480	26
Self-efficacy	General Self-Efficacy Scale, short form	6 items; 4-point Likert scale scored 1 – 4. Total sum score from 6 to 24.	Romppel M, et al. Psychosoc Med 2013; 10: Doc01.	27
Adverse life events	Life Events Checklist (LEC)	48 prespecified life events (good and bad). 4-point Likert scale addressing subjective impact.	Johnson JH, McCutcheon, S.M. Assessing life stress in older children and adolescents. In I.G. Sarason & C.C. Spielberger (Eds), Stress and anxiety 1980;7:111-25.	30/31
Miscellaneous/hypotheses generating	Child-Adolscent Perfectionism Scale (CAPS); Highly Sensitive Person Scale (HSP); Parentign Dimension Inventory (PDI); self-invented	a) 1 item addressing socially prescribed perfectionism (from CAPS): “Others always expect me to be perfect”, 1-5 Likert scale b) 2 items from HSP: Startling tendencies and affected by other people’s feeling tendencies c) 2 items from the PDI, both addressering parental control. d) 4 items self-invented (interoceptive awareness and positive expectancies): “The intensity of symptoms tells how dangerous a disease is”; “if you have a bodily complaint, every effort should be taken not to make it worse”; “it is important		25/28/29

to be attentive to bodily signals in order to discover early signs of disease”; “things often turns out to be more easy than I anticipated”.

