The overarching objective for this prospective cohort study on COVID-19 in adolescents is to study the long-term effects, with particular emphasis on post-infectious chronic fatigue. We hypothesise that children having undergone COVID-19 has a higher prevalence of PICF/CFS long after the acute infectious event; furthermore, that risk factors for PICF/CFS encompass a complex mixture of genetic vulnerability and psychosocial factors.

2. Material and methods

The design allows prospective as well as cross-sectional analyses

Adolescents (12-25 years) with confirmed SARS-CoV-2-infection are eligible for the present study (Table 1, Fig. 2). Inclusion will be based on informed consent from patients/next-of-kin. We assume a total number of 500 included cases. A follow-up control is scheduled 6 months after inclusion. This design enables prospective and cross-sectional analyses.

Risk factors for long-term complications will be analysed using regression modelling. Fatigue is defined as the primary endpoint. This sensation is operationalized using the Chalder Fatigue Questionnaire, which is known to have good validity and reliability in children.⁶ Relevant independent (explanatory) variables include (but are not restricted to):

- *Background:* Sex, age, ethnicity, previous medical history, smoking habits in family, presence of allergy/atopy, etc.
- *Initial clinical findings:* Symptom load/intensity, fever, routine blood haematology and biochemistry, etc.
- *Infectious load:* SARS-CoV-2 viral counts.
- *Immune function:* Increased general inflammation
- *Genetic predisposition:* Cf. below (Tab. 2) for a comprehensive list of candidate genetic markers
- *Questionnaire results:* Emotionality (depression/anxiety, emotional awareness), personality factors (neuroticism, worrying), perceived loneliness, and negative life events.
- *Autonomic cardiovascular control:* Increased sympathetic nervous activity, decreased parasympathetic nervous activity
- *Cognitive functions:* Increased verbal memory, attention bias towards disease-related words, reduced working memory

[figure not shown]

Table 1. Criteria for inclusion and exclusion**Inclusion criteria**

Positive SARS-CoV-2 test
 Age 12-25 years
 < 28 days since onset of first symptom

Exclusion criteria

Hospitalised because of COVID-19
 Pregnancy
 Lack of consent from patient/next-of-kin

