- *Biobanking:* Biobanking of blood samples (whole blood, plasma, serum, RNA, viable Peripheral Blood Mononuclear Cells (PBMC)) as well as urine, hair and fecal samples, for subsequent analyses (cf. below). Blood sampling will be obtained in a fixed sequence from antecubital venous puncture.

- *Questionnaire:* A composite questionnaire will chart clinical symptoms, as well as background, psychological and social variables, and will be used for diagnostic categorization according to different case definitions of CFS/ME. The Chalder Fatigue Questionnaire (CFQ) charts subjective experience of physical and mental fatigue, and has been extensively used in CFS research. In this study, the CFQ total linear score (i.e. the sum across all 11 items, each item scored on a zero to three Likert scale) is applied as the primary endpoint in prediction modelling. Furthermore, fatigue caseness is defined as a CFQ total dichotomous score of 4 or higher (each item scored 0-0-1-1). The Hospital Anxiety and Depression Scale (HADS) is a validated questionnaire for charting symptoms of depression and anxiety. It consists of 14 items rated zero to three on Likert scales, allowing computation of sub-scores for depression and anxiety symptoms. In the present study, these sub-scores as well as total sum score will be applied. The Life Event Checklist (LEC) is a validated questionnaire for assessing both positive and negative life events. The inventory lists 45 events; the respondents are asked to mark each of them as positive or negative, and grade their impact on four-point Likert scales. The Brief Pain Inventory (BPI) is a validated questionnaire for assessing pain. In this study,

the four BPI items assessing pain severity on ten-point Likert scales will be used to compute a total sum score; in addition, scores on a single item (average pain) will be reported. Cf. supplement for further information on questionnaire instruments.

- *Autonomic cardiovascular control*: A 5-minute ECG recording will be performed applying The Bittium Faro 360® device (Bittium Corporation, Oulu, Finland), enabling later heart rate variability analyses. In the frequency-domain, vagal (parasympathetic) activity is the main contributor to high-frequency (HF) variability of heart rate, whereas both vagal and sympathetic activity contributes to low-frequency (LF) variability. The LF/HF ratio is considered an index of sympathovagal balance.

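### Does the Body Vigilance Scale scoring rule in the Supplement, which as written tops out at 31 rather than 40, need a change to the plan?

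*Protocol*

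**What the plan says.** The Supplement's overview of inventories has one row for interoception, measured by the Body Vigilance Scale (BVS). It makes four statements:

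- the format: "4 items; 11 point Likert scales 0 – 10";
- a rescaling: "Score on item 3 should be divided by 10";
- the handling of the last item: "Scores on item 4: average among 15 sensations";
- the resulting range: "Total sum score range 0 to 40".

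The BVS is described nowhere else in the protocol. Section 2 (Material and methods) makes the Chalder Fatigue Questionnaire (CFQ) total the primary endpoint. It introduces the candidate predictors with "Relevant independent (explanatory) variables include (but are not restricted to"; neither the BVS nor interoception is in the list that follows.

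Two other entries have a similar mismatch. The TAS-20 row describes a seven-item index as "5-point Likert scale scored 1-5, total sum score range 7 to 49". For the Life Events Checklist (LEC), the Questionnaire paragraph in Section 2 says "The inventory lists 45 events", while the Supplement says "48 prespecified life events (good and bad".

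**The concern.** The division of item 3 is a scoring step, not just a label, and it sits beside a scale and a total that do not fit it. If item 3 were recorded 0-10 and divided as instructed, it would add at most one point and nearly drop out of the total. If it were recorded 0-100 and an analyst trusted the 0-10 label and skipped the division, it would swamp the other three items. In either case the BVS total would not be the quantity the table describes, and any association of interoception with fatigue would rest on a distorted score. The main text sends readers to this Supplement for details of the instruments, so an error here cannot be dismissed as lying outside the protocol.

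**Working it through.** **Inputs**, all from the BVS row: four items on 0-10; item 3 divided by 10; item 4 the mean of 15 sensations, so still 0-10; stated total 0-40.

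**Does the stated range follow?** Add the item maxima after the stated transformations:

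- As written: 10 + 10 + 10/10 + 10 = 31. The stated 40 is not reproduced.
- Item 4 summed instead of averaged: 10 + 10 + 1 + 15 × 10 = 171.
- Item 4 left out: 10 + 10 + 1 = 21.
- Item 3 recorded 0-100 and divided: 10 + 10 + 100/10 + 10 = 40.
- Item 3 recorded 0-10 and not divided: 10 + 10 + 10 + 10 = 40.

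Rereading item 4 does not give 40. Only two readings do. The first keeps both the division and the range, and needs only an exception for item 3 in the scale label. An 11-point scale is compatible with steps 0, 10, ..., 100. The second makes an explicit instruction pointless.

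**What would a misreading do?** Item 3's largest possible share of the total:

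| Item 3 recorded | Divided? | Maximum total | Item 3 share |
|---|---|---|---|
| 0-10 | yes | 31 | 1/31 = 3% |
| 0-100 | yes | 40 | 10/40 = 25% |
| 0-10 | no | 40 | 10/40 = 25% |
| 0-100 | no | 10 + 10 + 100 + 10 = 130 | 100/130 = 77% |

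The two distorted cases are also the two that miss the stated maximum of 40.

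**How different is the literal total in the 3% case?** Assume equal item SDs and a common inter-item correlation ρ; the protocol gives neither, so take ρ from 0 to 0.5. The correlation of x1 + x2 + 0.1·x3 + x4 with the plain sum is

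3.1(1 + 3ρ) / √[(4 + 12ρ)(3.01 + 6.6ρ)].

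The correlation of item 3 with the total is (1 + 3ρ)/√(4 + 12ρ) undivided and (0.1 + 3ρ)/√(3.01 + 6.6ρ) divided.

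| ρ | Literal vs plain total | Item 3 with plain total | Item 3 with literal total |
|---|---|---|---|
| 0 | 0.893 | 0.500 | 0.058 |
| 0.3 | 0.956 | 0.689 | 0.448 |
| 0.5 | 0.976 | 0.791 | 0.637 |

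Item 3 nearly vanishes only when the items are close to uncorrelated, an unlikely state for items meant to be summed. At ρ = 0.5 its correlation with the total falls from 0.79 to 0.64, and the two totals correlate 0.98.

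**The two neighbouring entries.** TAS-20 index: 7 × 1 = 7 to 7 × 5 = 35, so the printed upper limit is 49 - 35 = 14 too high. LEC: 48 - 45 = 3 events apart. Neither figure enters a scoring step. The TAS-20 sum comes from the recorded responses, and the LEC has as many events as the administered form lists.

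**The case for a change.** The best argument for acting is that the protocol does not leave BVS scoring open: it fixes a rule, and the rule contradicts itself. The table's ranges are evidently meant to be exact. CFQ 11 × 3 = 33, HADS 14 × 3 = 42, negative affect 5-25, neuroticism 0-24, worry 16-80, loneliness 20-80 and self-efficacy 6-24 all follow from their items; among the stated sum ranges only the BVS and TAS-20 index fail. The text nowhere says that item 3 runs to 100. A correction would cost one look at the form and a few words. Emotional awareness and negative life events, the constructs behind the other two slips, are named as predictors.

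Most of that stands as a description of the error. The arithmetic is certain, and the 0-100 reading is an inference. If the form did record item 3 on 0-10, either the division or the range would be wrong, and the document alone cannot say which. What does not follow is a consequence for the analysis. The scenarios that distort the score each need a further failure. The 77% case needs an analyst to see values up to 100 and ignore an explicit instruction to divide. The 3% case needs a form that only the doubtful label supports. Both contradict the printed range. Scoring takes place after data collection and can be redone from the item responses.

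**Conclusion.** The BVS row is internally inconsistent, 31 against 40, and this is a clerical slip. The division and the range support each other, and the scale label probably omits an exception for item 3. On that reading the written rule gives the intended 0-40 score, with item 3 carrying 25% of the maximum. This rests on the row's internal logic; the administered form (no. 21 in the questionnaire) would settle it and is not reproduced in the protocol.

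No endpoint, threshold, sample-size statement or named analysis uses the BVS range. The primary CFQ endpoint is untouched, and the BVS could enter only through the open-ended predictor list. The TAS-20 range and LEC count are misprints that change no score. Anyone scoring the questionnaires will have the form at hand and can tidy all three entries then. The design, data collection and analysis stay as planned.
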